MHPH is the city's major health facility. There is limited primary care infrastructure within the province, so patients rely on MHPH for the majority of their healthcare needs. As in other parts of the country, there is a large burden of both communicable and non-communicable disease, including HIV/AIDS, tuberculosis diabetes, cardiovascular disease, chronic respiratory conditions and trauma.

The ED receives approximately 150 presentations per day, and is staffed by one emergency physician, three registrars (specialists in training), five health extension officers (HEOs) and approximately thirty nurses. The ED has recently been redeveloped, and now includes four resuscitation bays, 16 acute beds and five short-stay beds. Basic pathology and radiology services are available.

Under current arrangements, the ED has no triage system and manual data collection processes are leading to gross under-reporting of presentation numbers. Major challenges for the ED include understaffing, a large burden of primary care patients and access block.

A new electronic database of ED patients has recently been implemented to capture basic attendance data. This system will facilitate data capture for the study.

Design

This study will utilise pre-post intervention methodology and will be prospectively registered as a clinical trial with the United States National Library of Medicine Clinical Trials Register at clinicaltrials.gov.

Pre-intervention

A new MHPH ED Patient Registration and Triage Form (PRTF) will be created to facilitate the new system and capture relevant data items, such as demographics and initial vital signs (Appendix 1). This form will be based on an existing MHPH ED discharge form, as well as a triage form successfully implemented in another Pacific setting.⁷

Data from the PRTF will be entered by ward clerks into the ED's electronic patient registration system (recently implemented as part of a hospital-wide data improvement project). This system forms part of the MHPH medical records database.

After a trial period of staff testing the new form, the PRTF will be implemented and baseline data captured in the database. During this period, the PRTF will not include any triage information (Appendix 1A). Based on a power calculation (see below), two months of pre-intervention data will be collected.

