In order to identify patients who meet inclusion criteria, as defined below, the PRTF will require the treating clinician to indicate whether the patient had one of the ten sentinel conditions (listed below).

Intervention

The intervention will comprise implementation of a new triage and patient flow system facilitated through staff training and clinical redesign.

The three-tier World Health Organization Triage Scale (WHOTS) will be used as the triage instrument. This tool, developed collaboratively by the WHO, International Committee of the Red Cross (ICRC) and Médecins Sans Frontières (MSF), incorporates features of the SATS but has been modified for application in a wide variety of RL settings. WHOTS documents are provided in Appendix 2.

At the end of the baseline data collection period, MHPH ED staff will be trained in the new system. A variety of ED clinicians (who will subsequently take on the triage role) will be the focus of this training program. This will include nurses, community health workers and health extension officers in order to provide flexibility in the staffing model. Triage training will be delivered by an experienced Australasian volunteer nurse(s) and comprise workshops on triage principles, paper-based scenarios and simulation exercises.

Signage will be introduced to facilitate the new system of flow, and the ED will begin utilising the version of the PRTF that incorporates triage data (Appendix 1B). The triage instrument will be piloted over a one-month period (approximately). Modifications will be made based on real-time feedback as well as observations by the visiting team.

Post-intervention

After completion of the trial period, the new triage and flow system will be implemented under the leadership of local clinicians. The ED registration database will be updated to capture triage category data.

For admitted patients, hospital length-of-stay (LOS) and inpatient mortality data will be obtained from the WHPHA medical records database. These patients will be identified by the patient's unique hospital identification number.

Outcomes

Primary objective

The primary outcome will be time-to-assessment (TTA) by an ED clinician for ten time-critical conditions:

- Severe trauma
- Major burns
- Severe head injury
- Ruptured ectopic pregnancy
- Septic shock
- Myocardial infarction
- Severe asthma/COPD
- Severe pneumonia
- Meningitis
- Appendicitis

Pragmatic definitions for these conditions are provided at Appendix 3.

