The primary outcome will also be analysed by the proportion of patients with these clinical syndromes that are seen within a clinically appropriate timeframe (defined as 15 minutes, as discussed below).

Secondary outcomes will include:

- Length of hospital stay
- ED mortality
- Inpatient mortality

These are also defined in Appendix 3.

Secondary objectives

Validity of the WHOTS will be assessed through its ability to predict ED outcomes. This will include the relationship between triage category and admission rates and ED mortality.

Under- or over-triage rates will also be calculated using disposition as a reference standard. This approach has limitations (see below) but is widely used in triage research.

Over-triage will be defined as the proportion of emergency (category 1) patients who are discharged. Under-triage will be defined as the proportion of non-urgent (category 3) patients who are admitted. Rates will be compared with the acceptable under- and over-triage rates recommended by ACS COT¹³ (and widely referenced in triage research) and then benchmarked against other published data. This approach has limitations (given that not all category 1 patients will require admission, and many category 3 patients could reasonably be expected to; recommendations for triage in trauma do not necessarily apply to other disease categories; and the performance targets provided by an American society do not necessarily apply to other contexts) but will be undertaken to enable comparison with other triage research from LMICs.

Reliability will be assessed through inter-rater agreement between two local triage nurses as well as a local nurse and independent expert triage nurse.

Analysis

All data will be obtained from the MHPH medical records database. Hospital medical records staff will export de-identified data into an Excel document, which will be provided to researchers and stored on a secure, password protected Monash University drive. All data will be analysed using Stata. No identifiable data will be available to the researchers.

Primary objectives

For the primary outcomes, Student's t-test will be used to compare the difference in TTA for the ten sentinel conditions (assuming parametric data). Chi-Square will be used to determine the difference in proportions of patients seen within 15 minutes.

For the secondary outcomes of ED mortality, hospital mortality and hospital LOS, Student's t-test or Chi-Square will be used as appropriate.

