Secondary objectives

For predictive validity, Chi-Square and correlation coefficient derived by Cramer's V will be used to investigate the relationship between triage category and admission rates & ED mortality.

Under- and over-triage rates will be calculated using the definitions above. Acceptable limits set by the American College of Surgeons Committee on Trauma (an under-triage rate of less than 10% and an over-triage rate of 30–50%) will be used as the reference standard.¹³ This approach is consistent with that used in other triage research, despite the limitations discussed above.^{9–12}

For reliability, the modified Kappa statistic will be used to test inter-rater agreement between triage nurses.

Sample size

It is estimated that approximately 15 patients per day present with one of the ten sentinel syndromes and wait an average of 20 minutes to be seen. A clinically significant improvement in the TTA for these patients is thought to be five minutes. Although Australasian guidelines recommend that high acuity presentations (equivalent to categories one and two in the Australasian Triage Scale) are seen within 10 minutes of arrival,¹⁶ a target of 15 minutes is thought to be acceptable in the resource limited context of MHPH.

Based on these figures, a sample size of 34 (17 per group) will be required to demonstrate a clinically significant decrease in TTA for the selected time-critical conditions at an alpha of 0.05 and beta of 0.8.

The primary outcome will also be analysed by the proportion of patients seen within 15 minutes of arrival. Assuming baseline performance is 45%, an absolute improvement of 10% (to 55%) will require a sample size of 784 (392 per group) at an alpha of 0.05 and beta of 0.8.

The secondary outcome of mortality will require a larger sample. In order to demonstrate an absolute reduction in mortality of 5% (from an estimated baseline mortality rate of 15%), a sample size of 1372 (686 per group) is required at an alpha of 0.05 and beta of 0.8.

To ensure a satisfactory sample size to demonstrate all outcomes, pre- and post-intervention periods of 8 weeks will be utilised. This is based on a total sample size of 1372 for the secondary outcome of mortality (with a buffer of 10%) at an estimated presentation rate of 15 per day. This requires pre- and post-intervention periods of at least 50 days.

Ethics

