Appendix 1A – Pre-intervention Patient Registration and Triage Form

Appendix 1B – Post-intervention Patient Registration and Triage Form

See attached.

Appendix 2

World Health Organization Triage Scale – user guidance

See attached.

Appendix 3

Definitions for primary and secondary outcomes

Definitions related to primary outcomes

- Major trauma – any injury requiring blood transfusion or an intercostal catheter in the ED, or transfer direct to the operating theatre
- Severe head injury – any patient with objective evidence of a head injury and a Glasgow Coma Scale less than nine
- Major burns – any burn of greater than 15% total body surface area, as estimated by the treating clinician
- Myocardial infarction – an ECG positive for ST-elevation myocardial infarction, or raised troponin based on the threshold defined by the local laboratory
- Septic shock - fever (temperature $>37.5^{\circ}\text{C}$) and hypotension (systolic BP $\leq 90\text{mmHg}$)
- Ruptured ectopic pregnancy – objective evidence of pregnancy (extra-uterine gestational sac on ultrasound or positive urine βHCG) and free fluid on ultrasound
- Severe asthma/COPD – any patient with an oxygen requirement where the most likely diagnosis is an exacerbation of asthma or chronic obstructive pulmonary disease
- Severe pneumonia – any patient with an oxygen requirement where the most likely diagnosis is pneumonia
- Meningitis – any patient where the most likely clinical diagnosis is meningitis
- Appendicitis - any patient where the most likely clinical diagnosis is appendicitis

Time to assessment - the time interval in minutes between patient arrival at ED reception and the time of first assessment by the treating clinician

Definitions related to secondary outcomes

- Length of hospital stay – the number of days from presentation to discharge
- ED mortality – any death that occurs while the patient was physically in the ED, excluding patients who meet criteria for ‘deceased on arrival’
- Inpatient mortality - any death that occurs while the patient was admitted to hospitals, excluding any deaths that occur in the ED

Deceased on arrival is defined as any patient who is obviously deceased on arrival, as determined by the treating clinician.

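### Could the new triage contact itself stop the time-to-assessment clock, because the stopping event is worded differently in different places?

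*Combined protocol and SAP*

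**What the plan says.** The stopping event for time to assessment (TTA) is described in three places.

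- **Outcomes, Primary objective.** "The primary outcome will be time-to-assessment (TTA) by an ED clinician for ten time-critical conditions". The same outcome is then analysed as the proportion of patients "seen within a clinically appropriate timeframe", set at 15 minutes.
- **Sample size.** Patients with a sentinel condition are said to "wait an average of 20 minutes to be seen". The next sentence gives the worthwhile improvement as five minutes of TTA.
- **Appendix 3, definitions related to primary outcomes.** TTA runs in minutes from arrival at ED reception to "the time of first assessment by the treating clinician".

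The Intervention section says of the training: "A variety of ED clinicians (who will subsequently take on the triage role) will be the focus of this training program". These staff are nurses, community health workers and health extension officers. The Setting section says that the department has no triage at baseline.

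On recording, the Pre-intervention section says "Data from the PRTF will be entered by ward clerks". From the intervention onward, "the ED will begin utilising the version of the PRTF that incorporates triage data". The two versions of the form (Appendix 1A and 1B) are attachments and are not reproduced in the text available for review.

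**The concern.** The Outcomes section ends the interval at assessment by a member of a staff group, and the Intervention section names that same group as the people who will triage. The word *seen* in the 15-minute analysis and in the sample-size section names nobody. Someone who read only those sections could let triage end the interval.

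That would matter because triage is the intervention and exists only in the second period. Any record closed at triage shortens the post-period time, with no counterpart at baseline unless early nurse contacts were counted there too. The error would run in one direction, in favour of the new system, and a larger sample would not remove it. The comparison is an uncontrolled before-and-after one, the form changes between periods, and clerks transcribe the times, so inconsistent recording could go unnoticed.

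**Working it through.** **1. The wordings side by side.**

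| Place | Who ends the interval | Status |
|---|---|---|
| Outcomes, primary outcome sentence | any ED clinician | general label |
| Outcomes, 15-minute analysis | not stated | same outcome, dichotomised |
| Sample size | not stated | used interchangeably with TTA |
| Appendix 3 | the treating clinician | formal definition: start, stop and unit |

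Only the last row is a definition. The first is broader but does not contradict it, since a treating clinician in the ED is an ED clinician. The middle two are not rival definitions. The Outcomes section introduces the 15-minute proportion as a further analysis of the primary outcome, and the Sample size section moves from waiting to be seen to TTA in consecutive sentences.

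**2. Who the treating clinician is.** The term has no entry of its own, but its use is consistent. This person marks the sentinel condition on the form (Pre-intervention), estimates burn area and determines whether a patient was dead on arrival (Appendix 3). Several sentinel definitions need a most likely diagnosis, an ECG or troponin, an ultrasound, or a transfusion. That is clinical work-up, not sorting at the door. Where the plan means triage staff as raters, it calls them triage nurses.

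**3. The plan's own figure.** For 45% against 55%, two-sided alpha 0.05, power 0.8 (the stated beta of 0.8 read as power), pooled variance and no continuity correction, the calculation gives 392 per group, or 784 in total. This matches the Sample size section. The figure does not depend on how the stopping event is worded.

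**4. What misreading would have to do.** Let *f* be the net share of records closed at triage: the post-period share minus the baseline share closed at an equivalent contact. Assume no true change in waiting and that the affected records are typical of all records. Eight weeks at 15 patients per day gives 8 × 7 × 15 = 840 records per period.

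*15-minute proportion.* Apparent gain = *f* × (*q* − 0.45), where *q* is the share of triage contacts within 15 minutes (assumed). For a gain of 0.10:
- *q* = 1.0: *f* = 0.10/0.55 = 0.182, about 153 of 840 records.
- *q* = 0.8: *f* = 0.10/0.35 = 0.286, about 240 records.

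*Mean TTA.* Apparent fall = *f* × (20 − *t*), where *t* is minutes from arrival to triage (assumed). For a fall of 5 minutes:
- *t* = 5: *f* = 5/15 = 0.33.
- *t* = 10: *f* = 5/10 = 0.50.

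At *f* = 0.10 the artefact is 0.10 × 0.35 to 0.10 × 0.55, or 3.5 to 5.5 percentage points, and 0.10 × 10 to 0.10 × 15, or 1.0 to 1.5 minutes. At *f* = 0, which is what Appendix 3 implies, both are zero.

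**The case for a change.** The strongest argument for a change is that Appendix 3 excludes triage only by implication. The Outcomes section sends the reader there for the ten conditions and the secondary outcomes, but not expressly for TTA. No sentence says that a triage contact does not count. Health extension officers are among the ED's clinical staff and are also trained to triage, so job title alone does not separate the two contacts. One who triaged and then treated the same patient would be a borderline case. The researchers receive a de-identified export and might not be able to tell afterwards which contact a recorded time represents. A modest misreading would also be enough: at *f* = 0.10 with every triage contact inside 15 minutes, the chance of a significant 15-minute result with no true change would be about 62% at 840 per period.

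The textual observations stand: the label is loose, the pointer is missing and the role is defined only through use. They do not show that the plan prescribes an unequal comparison. TTA is defined under the primary-outcome heading of the appendix in which the plan collects its outcome definitions. The functional sense of *treating* handles dual-role staff better than a list of job titles would. The 62% describes recording that departs from the plan's own definition, at a rate the documents do not suggest. The forms that would show whether triage time has its own field are not visible, so no fault can be inferred from them.

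**Conclusion.** No change to the plan follows. One formal definition exists, it applies to both forms of the primary outcome, and under it a triage contact does not stop the clock in either period. The comparison is then like for like and the size of the problem is zero. The break-even shares of 18% to 29% for the 15-minute proportion and 33% to 50% for mean TTA rest on assumed triage timings. They show what recording contrary to the definition would cost and are not evidence of bias in the plan.

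This conclusion assumes that Appendix 3 governs over the summary label, that *seen* means the same event, and that the treating clinician is identified by function. All three are the natural reading of the document as a whole. Repeating the appendix wording in the Outcomes section would be tidier, but it would record what the plan already implies and would alter neither the analysis nor the sample size.

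### The primary outcome is tested in two ways, each at 0.05, with no rule for which test decides; if either could be claimed, the false positive rate would be roughly 8% to 9%

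*Combined protocol and SAP*

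**What the plan says.** Under Outcomes, Primary objective, the protocol states: "The primary outcome will be time-to-assessment (TTA) by an ED clinician for ten time-critical conditions". After the list of conditions it adds: "The primary outcome will also be analysed by the proportion of patients with these clinical syndromes" that are seen within 15 minutes. The secondary outcomes follow in a separate list (length of stay, ED mortality, inpatient mortality), and the 15-minute proportion is not in it.

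Under Analysis, Primary objectives, two tests are given side by side: "For the primary outcomes, Student's t-test will be used to compare the difference in TTA for the ten sentinel conditions (assuming parametric data"), and then "Chi-Square will be used to determine the difference in proportions of patients seen within 15 minutes".

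Under Sample size, mean TTA needs 17 per group to show a "clinically significant decrease in TTA for the selected time-critical conditions at an alpha of 0.05 and beta of 0.8". The improvement in the proportion from 45% to 55% "will require a sample size of 784 (392 per group) at an alpha of 0.05 and beta of 0.8". In both places the beta of 0.8 can only mean 80% power.

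No section gives an order between the two tests, a division of alpha, a rule that both must be significant, or a statement that one of them is only supportive.

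**The concern.** Two tests carry the primary label, and nothing says which one answers the primary question or what is concluded when they disagree. Disagreement is the usual form of a false positive here. In a simulation with no true effect (lognormal model, described in the working), at least one test was significant in 8.6% of runs and both in 1.6%. So (8.6 − 1.6)/8.6, or about 81%, of the false positives had one test significant and the other not.

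If the choice is left until the results are known, the favourable test can be reported as the primary result, and the stated alpha of 0.05 no longer describes the risk of a false primary claim.

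**Working it through.** **Inputs from the protocol.** Alpha 0.05 for each test; 80% power; 45% against 55% seen within 15 minutes; baseline mean TTA 20 minutes; difference of interest 5 minutes; 8 weeks per period at 15 eligible patients per day, so 56 × 15 = 840 per period. The SD and distribution of TTA are not given.

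**1. Reproduce the plan's figures.** For the proportion, with pooled variance and two-sided 0.05:

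n = [1.960 × √(2 × 0.5 × 0.5) + 0.842 × √(0.45 × 0.55 + 0.55 × 0.45)]² / 0.10² = (1.386 + 0.592)² / 0.01 ≈ 391.3, rounded up to 392.

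This matches. A one-sided test would need 309 and alpha 0.025 would need 474, so the plan uses the full two-sided 0.05 here.

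For mean TTA, 17 per group reproduces only with an assumed SD. The normal approximation gives 5 / (√(2/17) × 2.802) ≈ 5.2. A t-test calculation with SD 5 gives 16.7, rounded up to 17.

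**2. Error rate if either test may be claimed.** With each test at level 0.05:

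P(at least one significant) = 0.05 + 0.05 − P(both significant).

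- Upper bound: 0.10.
- Independent tests: 1 − 0.95² = 9.75%.
- Correlated tests: 1 − P(|Z₁| < 1.96 and |Z₂| < 1.96), bivariate normal with correlation ρ. Under no effect, ρ is the absolute correlation between a patient's TTA and the indicator that TTA is at most 15 minutes.

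**3. ρ under assumed TTA distributions.** For the lognormal, mean 20 and 45% within 15 minutes require (ln 0.75 + σ²/2)/σ = −0.126. This gives σ = 0.643, median 16.3, SD 14.3 and ρ = 0.643.

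| Assumed TTA distribution | ρ | Either test significant |
|---|---|---|
| Lognormal, mean 20, 45% within 15 min | 0.643 | 8.6% |
| Gamma, mean 20, 45% within 15 min | 0.715 | 8.3% |
| Normal, mean 20, 45% below 15 min (SD 39.8) | 0.796 | 7.8% |
| Normal, mean 20, SD 5 to 5.2 | 0.66 to 0.67 | 8.5% |
| Exponential, mean 20 | 0.710 | 8.3% |
| Lognormal, mean 20, SD 5 to 40 | 0.49 to 0.65 | 8.6% to 9.1% |

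Simulations of 20,000 runs with 840 per period agree within simulation error: gamma 8.0%, lognormal 8.6% and 8.8% in separate runs, normal 7.9%. In the lognormal run that gave 8.6%, the t-test alone rejected in 5.0% of runs and the chi-square alone in 5.2%, so 5.0 + 5.2 − 1.6 = 8.6.

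**4. Why a range.** The plan's inputs do not fix one distribution. A normal TTA with mean 20 and the SD of about 5 implied by 17 per group puts only 16% to 17% of patients within 15 minutes, against the stated 45%. A normal TTA with 45% below 15 minutes needs an SD of about 40.

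**5. If both tests had to be significant**, the error rate would be at most 5%.

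**The case against.** The strongest reply is that there is one primary outcome, TTA, and the proportion merely shows it in another form. Much supports this:

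- The Outcomes section names TTA first and in the singular.
- The Limitations section speaks of a single primary outcome, and the Conclusion rests the study question on a decrease in TTA without mentioning the proportion.
- In Appendix 3, apart from the ten conditions, the only measure defined under the primary heading is time to assessment.
- The plural in the Analysis section is weak evidence. That subsection also has a plural heading for objectives, although the Aims set one primary objective.
- Sizing at 0.05 does not show co-primary status, because mortality, which is explicitly secondary, is sized in the same way.

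These points stand, and they rule out two stronger readings. A reader might infer that the plan sets up two co-primary endpoints, either of which wins; no sentence says so. A reader might also take 8.6% as the trial's actual error rate; that figure needs both an either-test rule and one assumed distribution, and the documents supply neither.

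The points do not close the gap. The proportion is called an analysis of the primary outcome, has its own test under the primary label, and is absent from the secondary list. Nothing makes it supportive. The correlation between the tests is already in the calculation; it reduces the inflation but does not remove it.

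It is also fair that the tests would seldom disagree if the planned effects occur: with 840 per period the proportion has 98.4% power and mean TTA nearly 100% at SD 14.3. That concerns power under a real effect and does not bear on the error rate when there is none.

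**Conclusion.** The point holds in a limited form. The plan puts two tests at 0.05 under the primary label and does not say how they combine. If either may be claimed, the false positive rate is roughly 8% to 9% (7.8% to 9.1% over the distributions tried) and at most 10%. If TTA alone decides, which is where the text leans, it is 5%; if both must succeed, it is at most 5%. The plan should say which applies.

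The range rests on assumed TTA distributions, two-sided tests, independent patients and no time trend. In an uncontrolled pre-post study, whose Limitations section already acknowledges confounding and changes in demand and staffing, the 5% for each test is itself an idealisation. The gap is worth closing before results are seen, mainly because doing so costs almost nothing.

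**What to change.** In Analysis, Primary objectives, change the plural to the singular and state:

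> The comparison of TTA between periods is the single primary analysis, at two-sided 0.05. The proportion seen within 15 minutes is a key secondary analysis, tested confirmatorily only if the TTA comparison is significant; otherwise it is reported descriptively.

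Bring the matching sentences in Outcomes and Sample size, and the heading in Appendix 3, into line.

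**Cost.** No extra patients are needed and TTA loses no power. The 15-minute result alone could not be claimed as a primary success, and its confirmatory test depends on TTA passing first. With 840 per period and a 5-minute difference, TTA power is 99.9% at SD 20 and about 73% at an extreme SD of 40, so the first step rarely blocks the second unless TTA is very dispersed. Because the t-test is conditional on parametric data, the TTA test should be fixed in advance so that the first step is unambiguous.

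**Alternative.** If the sponsor wants either result to support a primary claim, alpha can be split 0.025/0.025. The either-test error is then about 4.4% at ρ ≈ 0.64. The proportion needs 474 per group against about 840 expected, and its power at 840 falls only from 98.4% to 96.9%.

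### The under-triage rate is taken over all category 3 patients, so it does not show what share of time-critical patients are labelled non-urgent, and it can mislead in either direction

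*Combined protocol and SAP*

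**What the plan says.** In the combined protocol and SAP, the Secondary objectives part of Outcomes takes disposition as the reference and states: "Under-triage will be defined as the proportion of non-urgent (category 3) patients who are admitted". The Secondary objectives part of Analysis takes the trauma committee's limits as its standard, including "an under-triage rate of less than 10" per cent. The plan gives no expected value for the rate and no expected share of patients in category 3.

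The Outcomes section discloses limits of the approach. On admission, it says that "many category 3 patients could reasonably be expected to". It adds that trauma targets and American targets may not carry over. It keeps the approach so that results can be compared with other triage research from low- and middle-income countries. The remaining validity analyses (Chi-Square and Cramer's V) relate triage category to admission and ED mortality only.

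On volumes, Setting says "The ED receives approximately 150 presentations per day" and lists among the department's difficulties "a large burden of primary care patients and access block". Sample size estimates that "approximately 15 patients per day present with one of the ten sentinel syndromes".

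On data, the Pre-intervention section says that "the PRTF will require the treating clinician to indicate whether the patient had one of the ten sentinel conditions". The primary outcome is measured in these patients in both periods, so the flag must also exist after the intervention. The Post-intervention section says: "The ED registration database will be updated to capture triage category data".

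**The concern.** Under-triage, as a clinical reader understands it, is the share of patients who needed urgent care but were labelled non-urgent. The plan's rate answers a different question: of those labelled non-urgent, how many were admitted? Its denominator is likely to be several times larger than the number of time-critical patients, so a serious failure to recognise those patients can be diluted. Its numerator also counts stable patients for whom admission was reasonable and a non-urgent category was correct, so the rate can be high with no failure at all.

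The validity of this scale is a stated objective. The Conclusion says that no performance data have been published and that the results should inform use elsewhere. A figure above or below 10% will be read as evidence on missed urgent patients. The plan already defines ten time-critical conditions and records who has them, yet it does not report which category those patients received.

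**Working it through.** **Plan figures behind the inputs.** The plan computes no under-triage figure. Its 15 sentinel patients per day can be checked through the sample size that uses it. For mortality of 15% against 10%, two-sided alpha 0.05 and power 0.8, the usual two-proportion formula without continuity correction gives 686 per group (1372 in total), as stated. With the 10% buffer, 686 × 1.1 / 15 = 50.3 days, which matches the stated minimum of 50 days. Eight weeks is 56 days, so the post-intervention period should yield about 15 × 56 = 840 sentinel patients.

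**Formula.** Per day, let C = number in category 3 (assumed share × 150), m = share of the 15 sentinel patients placed in category 3 (all taken as admitted), and a = admission rate among the other category 3 patients.

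Plan's rate = [15m + a(C − 15m)] / C

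The largest a that keeps the rate within 10% is (0.10C − 15m) / (C − 15m).

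**Direction 1: rate too low.** Take m = 40% for illustration, so 15m = 6 per day. The category 3 share and a are assumptions, so both are varied.

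| Category 3 share | C per day | Rate if a = 0 | Rate if a = 3% | Rate if a = 5% | Ceiling on a |
|---|---|---|---|---|---|
| 40% | 60 | 10.0% | 12.7% | 14.5% | 0% |
| 50% | 75 | 8.0% | 10.8% | 12.6% | 2.2% |
| 60% | 90 | 6.7% | 9.5% | 11.3% | 3.6% |
| 70% | 105 | 5.7% | 8.5% | 10.4% | 4.5% |
| 80% | 120 | 5.0% | 7.9% | 9.8% | 5.3% |

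For example, at a 60% share with a = 3%: (6 + 0.03 × 84) / 90 = 8.52 / 90 = 9.5%. The limit is met while 6 of 15 sentinel patients, 40%, are labelled non-urgent.

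**Direction 2: rate too high.** Put m = 0. The formula reduces to a. If 10% or more of category 3 patients are admitted, the limit is missed at every category 3 share, with no sentinel patient misplaced.

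**Precision of a sentinel-based rate.** The half-width of the 95% CI is 1.96 × √[p(1 − p)/n].

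- n = 840, p = 10%: 1.96 × √(0.09/840) = 2.0 points
- n = 840, p = 40%: 1.96 × √(0.24/840) = 3.3 points
- n = 84 (840/10, the average per condition), p = 10%: 1.96 × √(0.09/84) = 6.4 points

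**The case against.** The strongest reply is that the plan chose this measure knowingly. It states that the approach has limitations, lists several, and keeps it for comparability; the background adds that there is no gold standard for urgency. This stands as a reason to retain the disposition-based rates. It does not answer the point, because the listed limitations do not include the denominator. The background's remark on urgency measures also does not explain leaving the trial's own marker out of the validity analysis.

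A second reply is that the 40% example is fragile. It is illustrative and comes from no figure in the documents. With 5% of the other category 3 patients admitted, the limit is missed at shares of 50%, 60% and 70%. Since the plan itself expects many category 3 admissions, a falsely high rate is at least as likely as a falsely reassuring one. This stands. A reader might infer that the scale is expected to pass while missing 40% of time-critical patients; the documents support only that this can happen under the conditions tabulated.

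Third, a reader might infer that the plan would declare the scale safe on this rate. It contains no such decision rule: the rates are compared with limits and benchmarked, alongside the Chi-Square and Cramer's V analyses. A reader might also assume that disposition is decided with the triage category in view. That is plausible, but the forms in Appendix 1 are not reproduced, and nothing here depends on it.

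Fourth, the sentinel flag is itself imperfect. The treating clinician sets it and may know the category. Several definitions in Appendix 3 rest on later tests, treatment or diagnosis, and the ten conditions are only some of the urgent patients. This stands, and it is why the sentinel-based rate should sit beside the existing one and not displace it.

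Finally, the primary outcome measures time to assessment in the same patients, so widespread mis-triage would tend to show there. It would not show by category, so it does not validate the scale.

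**Conclusion.** The point holds as a gap in the validity objective. The plan's rate does not estimate the share of time-critical patients labelled non-urgent, and a value on either side of 10% does not settle that question. A low value can coexist with a large miss only if the category 3 share exceeds 40% and other category 3 admissions are rare. A high value follows whenever those admissions reach 10%, regardless of how sentinel patients were triaged. The volumes are the plan's; the category 3 shares, the admission rates, the 40% and the admission of every misplaced sentinel patient are assumptions.

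The documents do not support the stronger reading that the disposition-based rate should be dropped or demoted in favour of a new main measure. The primary outcome is unaffected.

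**What to change.** Keep the disposition-based under- and over-triage rates for comparison with other research. Add, as a co-reported validity measure, the proportion of post-intervention sentinel patients assigned category 3, with a 95% CI, and show their full distribution over categories 1, 2 and 3. State that acceptable under-triage will not be concluded from the disposition rate alone.

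Report by condition only if the form records which condition applied. The text requires an indication that one of the ten was present, which might be a single yes/no. If condition is recorded, give the wider intervals shown above. A repeat restricted to objectively defined cases would need items such as troponin, ultrasound and transfusion, which the plan does not show to be in the database, so it should not be promised.

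The cost is one definition, one table and a sentence on interpretation, using two fields that the plan already says will be recorded. The limits of the sentinel flag (set by a clinician who may know the category, partly dependent on later information, covering only a subset of urgent patients) should be stated next to the result.
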